This study will investigate the effectiveness of this device in high school athletes playing a collision sport such as football. The use of helmets during such a high-risk sport will allow for collision measurement devices to be embedded in the helmet and will not affect play or fit of equipment. Athletes participating in this study will be randomly assigned to one of two groups: 1) Device wearing during the season or 2) Non-device wearing during the season. By the nature of the sport selected, it is likely this pilot study will primarily include males, however if any female meets inclusion criteria on the team selected, she will be included in this investigation. The helmets of all participants will be outfitted with an accelerometer which will measure the magnitude of every impact to the head sustained by the athlete. Effectiveness of the device will be determined via differences in longitudinal brain imaging and functional testing following competitive football participation. A subset of athletes who report a diagnosed concussion will also receive additional brain neuroanatomical and neurophysiological testing within a week following the diagnosed concussive event. At each of these time points participants will also undergo various neurocognitive assessments outlined below.

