**(2) PURPOSE OF STUDY:**

The purpose of the study is to monitor longitudinal changes in brain structure and function between the preseason and postseason, in a population of football playing athletes wearing the Device and compared to a similar population not wearing the device. Secondly, the purpose is to determine the protection of the device relative to amount and magnitude of sustained head impacts.

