**(6) SELECTION & RECRUITMENT OF PARTICIPANTS:**

The purpose of the present study is to generate pilot data for effect size estimation and power analysis for future study. The group size proposed in the aims was determined empirically based on previous neuroimaging studies and study designs reported in the literature. The sample size proposed in this pilot study will not warrant extensive statistical analysis to test the listed hypothesis. This study is expected to lead to an accurate estimate of effect size and variability so that future studies can be designed more rigorously.

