We will recruit up to 60 study participants. The participants (age 14-19 years old) will be recruited from a local school district and local sports clubs and teams. Participants will be recruited using a top-down approach. We have gained the consent and the cooperation of the school district administrations. Presentations and letters from the research team will be given to each participating school to detail the participation requirements and study risks. The high-risk sports which utilize helmets during competition will allow for measurement devices to be embedded in the headgear and will not affect play or fit of equipment. By the nature of the sports selected, it is likely this study will primarily include males, however if any female meets inclusion criteria on the team selected, she will be included in the investigation. Questions regarding participation will be answered during the presentations or through e-mail or phone. Participants will be contacted via telephone to further explain the study, answer any additional questions and to enroll them in the study. The participants and parents/guardians who voluntarily agree to participate will be scheduled to complete the pre-participation testing. The participant and parent/guardian will read and sign the "Consent to Participate in a Research Study" form, approved by the Institutional Review Board of Cincinnati Children's Hospital. If the participant and parent/guardian does not read or sign the form, they will not participate in the study. Once the potential study participants/school teams are identified, they will be allocated to one of two groups: 1) Device wearing during the season or 2) Non-device wearing during the season. This research does not mandate that the participant maintains participation in their sport. The desire to participate in the sporting event is an independent, personal decision separate from the decision to enter into this study. If any athlete chooses to stop participation in the sporting activity then they will also be withdrawn from the study, due to no longer meeting inclusion criteria.

Inclusionary criteria include:

- Normal healthy volunteer
- Able to provide written consent

- Must be 14 years or older and a participant on varsity level high school football team

Exclusionary criteria include:

- Unable to provide written consent
- History of neurological deficits, previous cerebral infarction, or severe head trauma as indicated through pre-season screening:

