### ***Data Analysis.***

Data processing and analysis will be performed using a series of existing software including FSL (FMRIB's Diffusion Toolbox in FSL Software, Oxford, UK), AFNI (Cox, 1996) , SPM (Statistical Parametric Mapping analysis package, Wellcome Department of Cognitive

Neurology, London, UK), DTIStudio (John Hopkins University, Baltimore, MD; Jiang et al., 2006), as well as additional customized software written in Matlab or IDL.

DTI data will first be subjected to preprocessing to correct for Eddy current and head motion artifact, followed by calculation of the three diffusion eigenvectors and eigenvalues. DTI measures, including fractional anisotropy (FA), mean diffusivity (MD), axial diffusivity (AD), and radial diffusivity (RD) will be calculated. The regions of interest will be manually determined in major white matter areas such as corpus callosum, internal capsule, and external capsule. After being normalized to a common template, voxel based group analysis can be performed to explore brain regions that present significant group difference or longitudinal changes. Fiber tracking can be performed to generate white matter tracts in different areas in the brain, e.g., cortico-spinal tract, different segments in corpus callosum, optic radiation, cingulum superior longitudinal fasciculus, and others.

Functional fMRI (resting state fMRI) will also be subjected to routine image pre-processing pipeline. Functional connectivity analysis will be performed, using the CONN toolbox, <http://www.nitrc.org/projects/conn/>) between all brain regions that are involved in the proper functioning of default mode network, sensory motor network, visual network, and a series of other networks that are known to be strongly functionally connected during resting state. SWI, HARDI and ASL BOLD will undergo standard image post-processing.

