**Statistical considerations.** The data analysis will begin with a review of descriptive statistics for all major variables and all major subgroupings of variables in the data set. For the inferential methods, we will use a number of different generalized linear modeling techniques, including linear regression models. All analyses will be conducted using SAS® version 9.3 (SAS Inst, Cary, NC), or Mplus (Muthén, 2007). Initial analyses will be undertaken to inspect data for errors, inconsistencies, and incomplete information. This will include examining the data with simple frequency tables and dot plots for univariate data and scatter plots and multi-way dot plots for bivariate and multivariate data. Data anomalies that cannot be resolved by the Biostatistical/data management team will be sent as queries via email to the project investigator for clarification and/or correction. During the verification process, outlying values will be corrected if necessary. Incomplete information will be corrected and the project investigator will receive updates. To summarize bivariate relationships among predictors and between predictors and outcomes, Chi-square of Fisher's exact test or Spearman's rank correlation coefficient, will be used, as appropriate. For reporting inferential statistics, such as differences in rates or means, 95 percent confidence intervals will be used extensively to quantify degree of clinical efficacy. Unless otherwise stated, statistical tests are considered two-sided and a .05 significance level is used. All models will be adjusted for potential independent predictor variables but will be limited to the number of predictors we can fit in a regression model while maintaining a valid and reliable model. Candidate predictors include amount of playing time, amount of practice time, previous mTBI, weight, age and height. Collinearity will be examined. Linearity assumptions will be checked and transformations examined. In those cases, a log transformation, polynomial terms, or restricted cubic splines will likely be used to relax the assumption of linearity in the regression models. We will remove the nonlinear terms or transformation only if the nonlinear test is non-significant with a  $p \geq .10$ . Additionally, overly-influential observations and distributional assumptions will be checked. Models will be interpreted graphically, predicted values will be examined, and appropriate significance tests will be utilized.

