**Statistical analyses.** - Statistical analysis of outcomes measures will be done using SAS®, version 9.3 (SAS Institute, Cary, NC) and SPSS statistical software (SPSS Inc, Chicago IL). Comparisons between the testing conditions (collar vs. no collar) will be made using Analysis of Covariance, in order to control for time (pre vs post season) and condition (collar versus no collar). We will also conduct correlation analysis to test the association between imaging biomarkers (as described above) with the results obtained from the impact surveillance. The collision indices,

including total number of collisions, number of collisions from front, back, left, right, top, bottom, G force, and timing of each collision will all be recorded and tested in the analysis. Secondary analysis to compare the intervention with no intervention and calculate the rates would involve a Poisson model, using an offset to account for the playing time and exposure to concussive impact for each of the study participants. We will calculate the rate and the associated 95% confidence interval. SAS®, PROC GENMOD will be used for analysis, which allows us to account for the fixed and random effects, use the appropriate link function, and the offset for amount of playing time exposure.

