### Simple Reaction Time

A repeated measures mixed-model design will be employed. A total of up to three groups (Device vs. no device vs concussion) will be examined using a 3 x 2 (group by time point; pre-season vs. post-season) ANOVA.

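### The general collar comparison names only time and condition, with neither the pre-season value nor a condition-by-time term, so it does not define an estimate of the difference in change

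*Combined protocol and SAP*

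**What the plan says.** The question is one of change over the season. Section (2) sets out to "monitor longitudinal changes in brain structure and function between the preseason and postseason" in device wearers against non-wearers, and section (1) adds that "Effectiveness of the device will be determined via differences in longitudinal brain imaging and functional testing following competitive football participation".

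The model for this is one sentence in section (9), Statistical analyses: comparisons of the two conditions "will be made using Analysis of Covariance, in order to control for time (pre vs post season) and condition (collar versus no collar".

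Four other places bear on it:

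- Section (9), Statistical considerations, adjusts all models for further predictors, as far as a stable model allows: "Candidate predictors include amount of playing time, amount of practice time, previous mTBI, weight, age and height".
- Section (9), Simple Reaction Time, does cross group with time: up to three groups "will be examined using a 3 x 2 (group by time point; pre-season vs. post-season) ANOVA". Oculomotor Measures uses the same kind of design.
- Section (9), Data Analysis, says of the DTI data that "voxel based group analysis can be performed to explore brain regions that present significant group difference or longitudinal changes", without giving a model.
- Section (6) says the sample will not justify extensive testing of the hypothesis, but also: "This study is expected to lead to an accurate estimate of effect size and variability".

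**The concern.** The sentence does not fix a model. Both named terms are categorical, and one of them, condition, is the comparison itself listed as something to control for. Two terms that would make the model answer the question in section (2) are absent: the pre-season value of the same outcome, and a condition-by-time interaction.

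For the DTI, fMRI, BNA and ImPACT outcomes this is the only between-arm model with named terms. These include the imaging measures on which section (1) says effectiveness will be judged. An analyst could follow the sentence faithfully and report a condition coefficient that is not the collar's effect on pre-to-post change. The effect size is what the pilot is meant to hand on to later studies.

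**Working it through.** The plan gives no effect size, SD, pre/post correlation or dropout rate, so there is no stated figure to reproduce.

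**Inputs from the documents.** Up to 60 participants (section 6); two-sided 0.05 and 95% confidence intervals (section 9); the same test battery before and after the season (section 8).

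**Assumptions.** 30 athletes per arm; SD 1 at each visit; pre/post correlation r = 0.5, 0.7 or 0.9; collar effect on change d = 0.5 SD; pre-season arm difference b = 0, its expectation under randomisation; independent athletes.

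**1. What the named terms estimate with complete pairs.** The arm difference is b before the season and b + d after it. An additive time-plus-condition model forces one common difference and averages the two:

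[b + (b + d)]/2 = b + d/2.

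With b = 0 and d = 0.5 this is 0.25 SD, whatever r is. Simulation agreed: about 0.25 for this model, and about 0.50 for both baseline-adjusted ANCOVA and the arm-by-time contrast.

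**2. With missing post-season visits.** Section (6) makes some loss likely: "If any athlete chooses to stop participation in the sporting activity then they will also be withdrawn from the study". Let a share m of post-season values be missing equally in both arms, unrelated to outcome. The weight on d becomes:

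- least squares: (1 − m)/(2 − m). At m = 0.2: 0.8/1.8 = 0.444, giving 0.22 SD.
- generalised least squares with exchangeable within-athlete correlation: (1 − m)/(2 − m + m·r). At m = 0.2: 0.8/1.90 = 0.421, 0.8/1.94 = 0.412 and 0.8/1.98 = 0.404 for r = 0.5, 0.7 and 0.9, giving 0.20 to 0.21 SD.

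**3. If that coefficient were used for planning.** Two-sample t-test, 80% power, two-sided 0.05: an effect of 0.50 SD needs 64 per arm. The 0.25 SD figure, divided by the matching SD of a two-visit average, sqrt((1 + r)/2), needs 190 to 240 per arm (table). Divided by the single-visit SD it needs 253. That is about 3 to 4 times as many.

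**4. What the two standard models would give.** Standard errors are sqrt(2(1 − r²)/30) for ANCOVA on the pre-season value and sqrt(4(1 − r)/30) for arm-by-time. Half-widths use t = 2.00.

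| r | SD of two-visit average | n per arm from 0.25 SD | ANCOVA half-width (SD) | Arm-by-time half-width (SD) |
|---|---|---|---|---|
| 0.5 | 0.87 | 190 | 0.45 | 0.52 |
| 0.7 | 0.92 | 215 | 0.37 | 0.40 |
| 0.9 | 0.97 | 240 | 0.23 | 0.23 |

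The arm-by-time variance is 2/(1 + r) times that of ANCOVA: 33% larger at r = 0.5 and 5% larger at r = 0.9.

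**5. Unit of allocation.** Section (1) assigns athletes. Section (6) speaks of participants or school teams, and Injury Surveillance in section (8) has the intervention provided to each team on a random basis. If allocation is by team, a real pre-season difference b is more plausible. ANCOVA then estimates d + b(1 − r), leaving 0.5b, 0.3b or 0.1b at the three correlations, while arm-by-time removes b. The half-widths in step 4 would also generally be too narrow.

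**The case against.** The strongest reply is that the sentence is loose rather than wrong. Naming two factors in prose does not say the model is additive. Section (2) states the question as change, and the reaction-time and oculomotor paragraphs show the authors crossing group with time when they go into detail. The list of candidate predictors is introduced as inclusive, so a baseline value could be added. Section (6) also disclaims extensive hypothesis testing.

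Much of this stands, and it limits the point:

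- A reader might infer that the plan will halve the collar effect. The documents do not support that. It requires the additive model to be fitted, its condition coefficient to be reported as the collar effect, and a later planner to use that number without looking at change. None of the three is written down.
- A reader might infer that the ANCOVA has no continuous covariate at all. Statistical considerations adds several to all models, such as weight, age and height. What is missing is the pre-season outcome.
- A reader might extend the point to reaction time and oculomotor measures. Their designs cross group with time, so it does not apply to them.
- A reader might suppose that post-concussion visits would be counted as post-season. Section (8) describes them as additional and separate testing, and the reaction-time design treats concussion as its own group.

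What the reply does not do is choose a model. Baseline adjustment and a group-by-time test are different analyses, with different precision and different handling of a pre-season imbalance, and the text selects neither. General descriptive statistics are no substitute: arm and visit are not named as subgroupings, and tabulated means alone give no confidence interval for the difference in change.

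**Conclusion.** The point holds as a specification defect in one sentence, affecting the DTI, fMRI, BNA and ImPACT comparisons. That neither term is named there is certain from the text. The size depends on the literal additive reading: the condition coefficient is b + d/2 with complete pairs, so half the effect on change when b = 0, and about 0.40 to 0.44 of it with an assumed 20% of post-season visits missing. The one-half does not depend on d or r. The planning figures and half-widths do rest on the assumed effect, correlations, equal arms and independent athletes.

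Pilot status softens the consequence for hypothesis tests but not for estimation, which is the study's stated product. It should be fixed before analysis.

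**What to change.** Replace the sentence with one model per measure that estimates the arm difference in change, reported with its 95% CI, and state which model is primary:

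- ANCOVA of the post-season value on arm and the pre-season value of the same measure, one row per athlete. This is the more precise choice if athletes are individually randomised.
- Or a repeated-measures model with arm, time, arm-by-time and within-athlete covariance, reporting the interaction. This matches the reaction-time and oculomotor designs.

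State that post-concussion visits stay out of this two-visit model. Reconcile the statements on the unit of allocation. If it is the team, report the arm-by-time estimate at least as a sensitivity analysis and allow for clustering in the standard errors.

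The cost of the model change is one sentence of analysis text. No new data are needed, because both visits use the same battery.

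### Every listed head-impact index is to be tested against the imaging biomarkers at .05, with no deciding pair, no multiplicity control and no exploratory label for these tests

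*Combined protocol and SAP*

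**What the plan says.** Section (9), Statistical analyses, first compares collar with no collar and then adds a separate analysis: "We will also conduct correlation analysis to test the association between imaging biomarkers (as described above) with the results obtained from the impact surveillance". Its list of impact indices runs "including total number of collisions, number of collisions from front, back, left, right, top, bottom, G force, and timing of each collision". Counted as written, that is one total, six directions, G force and timing, so nine. The commitment to test every one of them is explicit: "G force, and timing of each collision will all be recorded and tested in the analysis".

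The biomarkers are those of section (9), Data Analysis. For DTI, "DTI measures, including fractional anisotropy (FA), mean diffusivity (MD), axial diffusivity (AD), and radial diffusivity (RD) will be calculated", in regions "manually determined in major white matter areas such as corpus callosum, internal capsule, and external capsule". The same part adds fibre tracts, voxel-based maps, resting-state connectivity, SWI, HARDI and ASL/BOLD.

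The error rate comes from Statistical considerations: "Unless otherwise stated, statistical tests are considered two-sided and a .05 significance level is used". Nothing is stated otherwise for the impact correlations.

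Two other places matter. Section (2) gives the second aim: "Secondly, the purpose is to determine the protection of the device relative to amount and magnitude of sustained head impacts". Section (6) describes a pilot meant to supply effect sizes and variability for later studies, and says its sample size does not justify extensive testing of the hypothesis.

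**The concern.** These correlations form their own family of tests. They do not use the collar contrast, so naming a primary collar outcome would leave them untouched. Correction within a voxel map works across voxels for one exposure and does not reach across nine exposures.

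The directional counts are parts of the total count, so the list tests the same exposure whole and in pieces. With no index or biomarker chosen in advance, whichever pair crosses .05 can be reported as a finding, for example one impact direction with one diffusivity measure in one region.

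Selection on p < .05 also works against the pilot's own aim. An association picked out this way carries an inflated correlation into the planning of the next study.

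**Working it through.** The plan gives no family-wise error or power figure for these tests, so there is no stated figure to reproduce. Its only stated rate is .05, two-sided, per test.

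**Inputs from the document**
- Indices: 9 (section (9), Statistical analyses).
- DTI measures: 4. Regions named as examples: 3. So 4 x 3 = 12 illustrative DTI outcomes (section (9), Data Analysis).
- Per-test level: .05 (Statistical considerations).
- Sample: up to 60 (section (6)).

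**Assumptions not in the document**
- The number of biomarkers tested: 1, 4 or 12.
- A common correlation among indices, and the same value among biomarkers, from 0 to 0.9.
- All 60 athletes have complete data.

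**Independent tests.** P(at least one) = 1 - (1 - .05)^m, and expected false positives = .05 x m.
- m = 9: 1 - .95^9 = 37.0%, expected 0.45.
- m = 9 x 4 = 36: 1 - .95^36 = 84.2%, expected 1.8.
- m = 9 x 12 = 108: 1 - .95^108 = 99.6%, expected 5.4.

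**Correlated tests.** Simulation with n = 60, no true association, Pearson tests at two-sided .05 and 6,000 data sets per setting. Entries are the chance of at least one p < .05.

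| Correlation within each set | 9 x 1 | 9 x 4 | 9 x 12 |
|---|---|---|---|
| 0 | 37% | 84% | over 99% |
| 0.3 | 32% | 77% | 98% |
| 0.5 | 28% | 66% | 91% |
| 0.7 | 21% | 45% | 68% |
| 0.8 | 16% | 34% | 51% |
| 0.9 | 13% | 21% | 29% |

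The expected number of false positives does not depend on the correlation. It stays near 5.4 for the 9 x 12 grid.

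**Sensitivity**
- Building the total from the six directions, and MD and FA from AD and RD, gave 51% to 92% for 9 x 12, with index correlation from 0.9 down to 0.3.
- Timing of each collision is not one value per athlete. Without it (8 x 12), the chance is 99% at correlation 0, 89% at 0.5, 47% at 0.8 and 28% at 0.9.
- Each test's null rate is .05 at any sample size, so losing athletes to MRI contraindications (section (8)) does not reduce these figures.

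**Size of a selected correlation.** At n = 60 the critical t on 58 degrees of freedom is 2.00. The critical |r| is therefore 2.00 / sqrt(58 + 2.00^2) = 2.00 / 7.87 = 0.25. Any null association reported as significant would show |r| above about 0.25.

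**What a restriction achieves.** One named pair is one test, at 5%. Naming only the index is not enough: over 12 independent biomarkers the chance is 1 - .95^12 = 46.0%, and over 4 it is 1 - .95^4 = 18.5%. Bonferroni over 108 tests would need .05/108 = .00046.

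**The case against.** The strongest reply is that this is a declared pilot. Section (6) disclaims extensive testing, and Statistical considerations promises wide use of 95% confidence intervals. The correlations also enter as an addition to the collar comparison. This softens the consequence, but the .05 default still applies to these tests, so the two sections pull in different directions.

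Three stronger readings are tempting, and the document does not support them.

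- A reader might infer that a chance correlation would give a false answer to the second purpose. Section (2) asks about device protection relative to impacts. A correlation without an arm term cannot show protection, whether it is true or false.
- A reader might infer that at least 108 tests are planned and that a false positive is therefore probable. The plan does not spell out a full grid, and the three regions are only examples. The chance falls to 29% for 108 tests at correlation 0.9 and never exceeds about 37% for one biomarker. High correlation is plausible, because directional counts make up the total and the DTI measures are related.
- A reader might take accumulated g-force with RD as a pair already established by the hockey study (section (3), Summary of Prior Work, item E). There the g-force correlation was with ERP network change in the non-intervention group. RD is reported only as a change over time.

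**Conclusion.** The point stands as a gap in the analysis plan that should be closed before the data are analysed. The stated rule tests all listed indices at .05 each, with no deciding pair, no multiplicity control and no exploratory label, in a pilot that itself disclaims extensive testing.

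Even the mildest case examined, one biomarker with indices correlated at 0.9, gives about 13%, roughly 2.5 times the nominal 5%. No single percentage should be quoted as the trial's error rate, because the range depends on correlations and a biomarker count that the document does not give. The consequence is confined to the impact-imaging associations. It does not extend to a claim of device protection, and it is separate from the collar comparisons.

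**What to change.** In section (9), Statistical analyses, state that the index-by-biomarker correlations are exploratory and will be reported as estimates with 95% confidence intervals, without claims of significance at .05. Also state how G force and timing are reduced to one value per athlete.

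If p-values are wanted, use a max-statistic permutation over the whole grid. Keep each athlete's imaging outcomes together and permute the impact records within arm, and within team if allocation was by team. Sections (6) and (8) refer to teams, whereas the Abstract describes athletes being assigned. Free permutation across all athletes would ignore that structure.

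If one association is to be tested at .05, name in advance one cumulative impact index (for example accumulated g-force) and one imaging change in one region or summary (for example RD). Present it as a new choice, not as a pair shown in the hockey study. To address the second purpose, model that change on impact, arm and the arm-by-impact interaction.

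The cost is a few sentences and, if chosen, one permutation run. No new data are needed. The downside is that directional and other secondary associations can no longer be called significant at a nominal .05.
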